5.5. Monitoring of compliance

The drugs will be sent to investigators (GPs in private practice). The treatment beginning two months before the expected grass pollen peak, the investigator will deliver it to the patient for 3 months (3 boxes) at V0, then for three other months at V1.

The investigator will ask the patient to bring back drug boxes (full and empty blisters) at each visit.

The counting of the remaining capsules will be made by the investigator. In case the patient would come in consultation a few days before the end of the treatment period, the patient will be allowed to keep the blister to complete the sequence.

A global compliance will be calculated for each patient on the total duration of treatment. Global compliance will be acceptable if it is between 80% and 120%. If values <80% or> 120%, the patient will be eliminated from the analysis according to the protocol and will be taken into account in the analysis by intention to treat.

5.6. Labelling and packaging of investigational medicinal products

The sponsor Labo'Life will provide drugs to investigational centres.

The labelling and packaging will be handled by Labo'Life according to Good Manufacturing Practice Annex 13.

At the end of the study, Labo'Life will recover the remaining treatments and ensure their destruction.

Drug storage conditions

- In the investigational centre: at room temperature, in its original packaging and in a locked cabinet.
- At patient's home: at room temperature, in its original packaging and out of reach of children.

6. Conduct of the study

6.1. Study procedures

The following demographic data will be collected during the first visit: date of birth, gender, ethnic group, weight, height, smoking habits and alcohol use status.

Medical history, treatment history, concomitant treatments and patient's physical examination will also be documented during V0.

The allergy must be confirmed by positive skin test and/or the presence of IgE for grasses (prick test defined as positive if higher than or equal to half the negative control; IgE are positive if at least class 3 (\geq 3.5 kU/L); these tests must have been made at the latest during the first visit.

A patient diary will be given to each patient.

- For evaluation of the total 5 symptoms score T5SS and rescue medication RS, it is essential that patients note **every day** the symptoms (sneezing, rhinorrhoea, nasal pruritus, itching and/or eye tearing and nasal obstruction) intensity, and the rescue medications, in their patient diary.
- It is also essential that the patient takes note **every day** of his/her QoL by filling in three questions included in his/her diary card: Did you sleep well? Can you work normally? How do you feel?
- It is also imperative that patients note the date of the start of treatment and the date of onset of symptoms.

This patient diary will be given to the patient at each visit, and will be brought back at the next visit, it will be reviewed and validated by the investigator and will be part of the CRF (Case Report Form).

All relevant (related to allergy) concomitant medications (except rescue medications) taken by the patient during the study period will be recorded at each visit in the CRF.

The AEs and SAEs will be recorded at V1 and V2 in order to assess safety.

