6.2. Study schedule

Study flow chart

	Screening (– 1 month)	V0 (2 months before grass pollen peak)	V1 (3 months after V0)	V2 (6 months after V0 or end of grass pollen peak)
Selection of patients Verification of inclusion/exclusion criteria Performance of allergy tests if needed	•			
Give information about the study Give the Inform Consent Form to the patient	•			
Eligibility check		•		
Signature of the Informed Consent Form		•		
Randomization		•		
Demography		•		
Medical history		•		
Physical examination		•	0	0
Allergy treatment history		•		
Delivery of treatment for 3 months		•	•	
Distribution of the patient diary		•	٠	
Start of treatment		•		
Diary card filling by the patient		•	•	•
Patient diary card control			•	•
Compliance control			•	•
Relevant (allergy-related) concomitant medications (except rescue medications)		•	•	•
Safety control (AE/SAE)			•	•
Study conclusion				•

• Compulsory • Optional

6.3. Identification of all the data sources that are not in the medical file

All data collected in the CRF have to be recorded in the patient medical file.

Patient diary data are source data which will be directly captured by the data management.

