8.2. Safety endpoints

Collecting data and analysis of safety endpoints described above will be performed by spontaneous statement or during monitoring.

An SAE report form will be attached to the CRF (collecting symptoms, dates, evolution, judgment of causality by the physician, actions taken)

All AEs / SAEs / SARs / SUSARs will be subject to coding in terms of System Organ Class and Preferred Terms, using the latest version of the dictionary MedDRA (Medical Dictionary for Regulatory Activities).

8.3.List of expected AEs

In the framework of this study, expected AEs are those mentioned in the SPC:

- In exceptional cases, it may appear dyspepsia when taken fasted (in this case, the granules will be taken one hour after the meal)
- Difficulties in falling asleep can occur if taken after 16 hours
- As with all homeopathic treatment, print of worsening symptoms can occur, that usually disappears after a few days.

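### Adverse events are actively collected only at two visits about three months apart, and the stated diary content has no adverse-event item, so mild, short-lived, non-allergic events are likely to be under-recorded and poorly dated

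*Protocol*

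**What the plan says.** On timing, section 6.1 of the protocol states: "The AEs and SAEs will be recorded at V1 and V2 in order to assess safety". The flow chart in 6.2 agrees: the safety control is marked only at "V1 (3 months after V0)" and "V2 (6 months after V0 or end of grass pollen peak)".

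On the route, 8.1 requires every adverse event in the study, whether seen by the physician or reported by the patient, to be entered in the CRF. Section 8.2 says that collection "will be performed by spontaneous statement or during monitoring". Section 8.4 requires SAEs to be reported within 24 hours of the investigator becoming aware of them.

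On the diary, 6.1 asks for daily entries on allergy symptoms and rescue treatment ("sneezing, rhinorrhoea, nasal pruritus, itching and/or eye tearing and nasal obstruction) intensity, and the rescue medications, in their patient diary"), three daily questions ("Did you sleep well? Can you work normally? How do you feel?"), and the dates of treatment start and symptom onset. Of the completed diary it says that "it will be reviewed and validated by the investigator and will be part of the CRF (Case Report Form)".

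The expected reactions in 8.3 are dyspepsia on fasting intake, difficulty falling asleep after late intake, and an impression of worsening: "print of worsening symptoms can occur, that usually disappears after a few days". Section 2.2 makes the frequency, severity and causality of AEs and SAEs a secondary endpoint.

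**The concern.** A patient with three days of dyspepsia in the first week would first be asked about it at V1, about 12 weeks later. Unless the patient had volunteered it, the record would rest on memory. V0 is two months before the expected pollen peak and V1 three months after V0, so V1 falls about one month after the peak (3 − 2 = 1). The patient must then separate an early minor complaint from most of a pollen season.

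At stake are the AE frequencies and the onset dates on which causality judgements lean. Section 1.3 already describes the product as perfectly tolerated, with no side effects reported. A low count obtained largely from unprompted report and three-month recall could not test that statement, yet might be read as confirming it. How events come to be known is a data-collection rule, so an analysis plan cannot repair it afterwards.

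**Working it through.** **1. Does another provision close the gap?**

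- Section 8.1 governs what is recorded once an event is known. It does not say how a non-serious event becomes known.
- Section 8.2 supplies the route between visits: spontaneous statement, which is unprompted, or monitoring, which can find only what has been written down.
- Section 8.4 applies to SAEs and starts from the investigator's awareness.
- Physical examination is optional at V1 and V2 (6.2), and only allergy-related concomitant medication is recorded (6.1, 6.2). A remedy taken for dyspepsia or poor sleep would leave no CRF trace.

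**2. Which expected reactions leave a daily trace in the stated diary content?**

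| Expected reaction (8.3) | Diary counterpart (6.1) | Step that makes it an AE record |
|---|---|---|
| Impression of worsening symptoms | Five daily symptom scores | None stated |
| Difficulty falling asleep | Daily sleep question | None stated |
| Dyspepsia | None specific; at most the general well-being question | None stated |

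For the first two, a dated daily record exists and the investigator reviews it. What is missing is a rule that turns an entry into an AE with severity, causality and dates. For dyspepsia, and for any other non-allergic complaint, there is no specific entry at all.

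**3. Size, as an illustration only.** The protocol gives no AE rate, recall rate or safety precision, so there is no figure to reproduce. Inputs: n = 50 per group (section 4.1); capture share s, assumed.

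If the true incidence is p and a share s of affected patients is captured, the recorded incidence is s × p. With no event recorded, the one-sided upper 95% bound solves (1 − s × p)^50 = 0.05, so

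p = [1 − 0.05^(1/50)] / s = 0.058 / s.

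| Capture s (assumed) | Upper bound for true incidence |
|---|---|
| 100% | 5.8% |
| 70% | 8.3% |
| 50% | 11.6% |
| 30% | 19.4% |

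Expected recorded cases per group are 50 × p × s. The chance of recording at least one is 1 − (1 − p × s)^50. Power is for separating true risks of 20% and 5% with 50 per group, two-sided 5% level. The risks are also assumed.

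| Capture s | Cases at p = 10% | Cases at p = 5% | Chance of at least one at p = 5% | Power, 20% v 5% |
|---|---|---|---|---|
| 100% | 5.0 | 2.5 | 92% | 62% |
| 80% | 4.0 | 2.0 | 87% | 52% |
| 50% | 2.5 | 1.25 | 72% | 34% |

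**4. Direction.** With equal capture in both arms the recorded difference is s × (p1 − p2), while the ratio (s × p1)/(s × p2) stays at p1/p2. Absolute frequencies, differences and power fall; neither arm is favoured.

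**The case against.** The strongest reply is that the protocol does not confine AE recording to two visits. Sections 8.1 and 8.2 admit patient reports at any time, SAEs have their own rapid route, and 5.2 tells patients to see a doctor for diarrhoea or persistent worsening. The centres are general practices. A reader of 6.1 might infer that AEs, including SAEs, can be recorded only at V1 and V2. Read with 8.1 to 8.4, the text does not support that; V1 and V2 are the scheduled collection points, not the only route.

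It is also fair that the transient worsening in 8.3 is a poor example of an event lost to recall, because allergy symptoms are scored daily and sleep has its own question. That stands. What remains for those two is the missing step from diary entry to AE record. Dyspepsia has no such counterpart, though the protocol calls it exceptional.

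The diary card is not shown, and 6.1 does not claim that its list is complete, so the card may already have a comment line. The point rests on the content as the protocol states it.

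Lastly, visit-based collection plus spontaneous reporting, for a product marketed since 2002, is a defensible choice. This limits the weight of the point but does not remove it: the endpoint is declared, and a daily instrument that could serve it is already in use.

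**Conclusion.** The point holds in a limited form. Non-serious AEs are actively sought only at V1 and V2, about three months apart. Between those visits collection depends on unprompted report, and the stated diary content offers no place for an adverse event. Mild, short-lived, non-allergic events are likely to be under-recorded and poorly dated. Entries on worsening and sleep exist, but nothing carries them to an AE record.

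The size cannot be derived from the protocol. The bounds of about 8%, 12% and 19%, against 5.8% with full capture, rest on assumed capture of 70%, 50% and 30%, on 50 patients in the group, and on a hypothetical zero count. They apply to event types that depend on recall, not to every AE.

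A reader might go further and infer that the plan is bound to show no side effects, or that it tilts the safety comparison towards the active product. Neither follows. Persistent, serious, volunteered or diary-visible events would still surface, and blinding makes a similar loss in both arms the reasonable expectation. The primary endpoint is unaffected.

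**What to change.** Add one dated line to the diary card, for example: *Any health problem today other than the symptoms scored above?* State that rhinitis or conjunctivitis symptoms already scored in the T5SS are not entered on this line; otherwise it will duplicate the efficacy data. At the diary control already scheduled for V1 and V2, the investigator reads this line together with the sleep and general well-being entries and transcribes adverse events to the AE page with onset and stop dates.

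Reword 6.1 to agree with 8.1 to 8.4, for example: *AEs are collected continuously from V0 through the diary and spontaneous reports and are recorded in the CRF at V1 and V2; SAEs are reported as in section 8.4.* If the card already carries such a line, only the review step, the T5SS rule and this sentence are needed.

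The cost is a change to the card before printing and ethics submission, with no added visit, staff or procedure. The downside is extra material: a daily diary for about 180 days in 100 patients is roughly 100 × 180 = 18,000 patient-days. The line will be blank on most of them, but some minor entries will need double entry, review and MedDRA coding.

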6.2. Study schedule

Study flow chart

	Screening (– 1 month)	V0 (2 months before grass pollen peak)	V1 (3 months after V0)	V2 (6 months after V0 or end of grass pollen peak)
Selection of patients Verification of inclusion/exclusion criteria Performance of allergy tests if needed	•			
Give information about the study Give the Inform Consent Form to the patient	•			
Eligibility check		•		
Signature of the Informed Consent Form		•		
Randomization		•		
Demography		•		
Medical history		•		
Physical examination		•	0	0
Allergy treatment history		•		
Delivery of treatment for 3 months		•	•	
Distribution of the patient diary		•	٠	
Start of treatment		•		
Diary card filling by the patient		•	•	•
Patient diary card control			•	•
Compliance control			•	•
Relevant (allergy-related) concomitant medications (except rescue medications)		•	•	•
Safety control (AE/SAE)			•	•
Study conclusion				•

• Compulsory • Optional

6.3. Identification of all the data sources that are not in the medical file

All data collected in the CRF have to be recorded in the patient medical file.

Patient diary data are source data which will be directly captured by the data management.

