Up Inclusion criteria	 Treatment set up two months before traditional pollen peak, then visits at 3 months and 6 months, or end of the peak. Age ≥18 years, male and female Woman of childbearing age using effective contraceptive means Patient having the faculties to understand and respect the constraints of the study Symptomatic since at least two seasons and confirmed by positive skin test and/or the presence of IgE for grasses (prick test defined as positive if higher than or equal to half the negative control; IgE positive if at least class 3 (≥ 3.5 kU / L); these tests must have been performed at the latest at the first screening visit Signature of the Informed Consent Form Pregnant woman or woman wishing to become pregnant Breastfeeding woman
Up Inclusion criteria	 Treatment set up two months before traditional pollen peak, then visits at 3 months and 6 months, or end of the peak. Age ≥18 years, male and female Woman of childbearing age using effective contraceptive means Patient having the faculties to understand and respect the constraints of the study Symptomatic since at least two seasons and confirmed by positive skin test and/or the presence of IgE for grasses (prick test defined as positive if higher than or equal to half the negative control; IgE positive if at least class 3 (≥ 3.5 kU / L); these tests must have been performed at the latest at the first screening visit Signature of the Informed Consent Form Pregnant woman or woman wishing to become pregnant Breastfeeding woman Patient with an acute exacerbation of allergic rhinitis
Up Inclusion criteria	 Treatment set up two months before traditional pollen peak, then visits at 3 months and 6 months, or end of the peak. Age ≥18 years, male and female Woman of childbearing age using effective contraceptive means Patient having the faculties to understand and respect the constraints of the study Symptomatic since at least two seasons and confirmed by positive skin test and/or the presence of IgE for grasses (prick test defined as positive if higher than or equal to half the negative control; IgE positive if at least class 3 (≥ 3.5 kU / L); these tests must have been performed at the latest at the first screening visit Signature of the Informed Consent Form Pregnant woman or woman wishing to become pregnant Breastfeeding woman Patient with an acute exacerbation of allergic rhinitis Patient with uncontrolled asthma

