9.4. Ethical considerations

Written informed consent:

The entire informed consent process involves giving a participant adequate information concerning the study, providing adequate opportunity for the participant to consider all options, responding to the participant's questions, ensuring that the participant has understand this information, obtaining the participant's voluntary agreement to participate, and continuing to provide information as the participant or situation requires. To be effective, the process should provide ample opportunity for the investigator and the participant to exchange information and ask questions.

The investigator undertakes to inform the patient clearly and after taking time for reflection the patient will sign and date the Inform Consent Form (ICF). The investigator must also sign and date the ICF.

Both documents will be issued on paper in 2 copies so the patient and the investigator can each keep a copy. The original one is for the investigator and will be archived in the Trial Master File.

Ethics Committee:

The sponsor undertakes to submit the study protocol, the diary card and the EQ-5D scale to the prior approval of the Ethics Committee.

Amendments to the protocol: change requests will be sent for authorization in accordance with current legislation, by the sponsor, to the competent authorities. The modified protocol will then undergo an updated version dated.

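### Allergy tests still needed for eligibility are scheduled at Screening, but consent is signed only at V0, so a study-driven test could precede consent

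*Protocol*

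**What the plan says.** Proof of grass sensitisation is mandatory. Section 6.1 states: "The allergy must be confirmed by positive skin test and/or the presence of IgE for grasses".

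The protocol gives the timing of the tests and of consent in several places:

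- **Section 6.2, flow chart, Screening column (one month before V0).** One merged row covers patient selection and "Verification of inclusion/exclusion criteria Performance of allergy tests if needed". Its only mark is at Screening. The next row, "Give information about the study Give the Inform Consent Form to the patient", is also marked only at Screening.
- **Section 6.2, flow chart, V0 column.** "Signature of the Informed Consent Form" has its only mark here, alongside the eligibility check and randomization.
- **Synopsis and section 4.2.** The inclusion criterion sets the deadline: "these tests must have been performed at the latest at the first screening visit".
- **Section 6.1.** The deadline is worded differently: "these tests must have been made at the latest during the first visit".
- **Section 9.4.** The consent process includes "providing adequate opportunity for the participant to consider all options", and "after taking time for reflection the patient will sign and date the Inform Consent Form". It does not say that signature comes before study-specific tests, and it describes no separate consent for screening.

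**The concern.** Handing over the form at Screening and collecting the signature at V0 gives the candidate time to reflect, which section 9.4 asks for. The difficulty is that a test needed to establish eligibility falls inside that reflection period. A candidate without an earlier prick-test or IgE result could have a skin or blood test done for the trial while still deciding whether to take part.

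What is at stake is participant protection and site conduct. A site that follows the flow chart and section 4.2 to the letter could perform a study procedure without documented consent. A site that waits for the signature would miss the deadline in section 4.2.

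**Working it through.** No arithmetic beyond counting marks applies; the check sets the provisions side by side.

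**Step 1: order in the flow chart (6.2).**

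| Activity | Screening (1 month before V0) | V0 |
|---|---|---|
| Criteria verified; allergy tests where needed | marked | – |
| Information given, consent form handed over | marked | – |
| Eligibility check | – | marked |
| Consent form signed | – | marked |
| Randomization | – | marked |

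The row containing the tests has one mark, at Screening. The signature row has one mark, at V0. Signature marks at or before Screening: 0. The nominal interval is one month. No visit window is stated, so the actual gap could be shorter.

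**Step 2: does the eligibility text allow a later test?** Under the synopsis and section 4.2 the tests must be done by the first screening visit. With signature at V0, every test that meets this deadline precedes the signature. Under these two statements, no test can be both on time and after consent.

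**Step 3: does section 6.1 change this?** Its deadline refers to the first visit. The same section collects demography at the first visit, and the flow chart marks demography only at V0, so V0 is a plausible meaning. A test at V0 after signature would then be on time under 6.1. It would still be late under the synopsis and 4.2, and the flow chart has no test mark at V0. Section 6.1 therefore conflicts with the other provisions and does not override them.

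**Step 4: does any other text supply consent earlier?** Section 9.4 gives the sequence information, reflection, signature, without tying it to the tests. No section says that a test done at Screening is routine care.

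**Step 5: who is affected?** Only candidates without an existing qualifying result, since the tests are performed only where needed. The protocol does not give their number, and none is assumed here.

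One further sign that the sequence was not worked through: section 4.2 lists the signed consent form as an inclusion criterion, yet the flow chart has the criteria verified at Screening, before a signature is scheduled.

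**The case against.** The strongest counter-argument has four parts.

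1. **Section 6.1 probably means V0.** On that reading a test after signature is allowed. This is a fair reading, but it leaves three places (synopsis, 4.2 and 6.2) pointing to Screening and adds an inconsistency between 4.2 and 6.1.
2. **Section 4.2 sets a deadline and does not schedule a procedure.** This is correct; only the flow chart schedules the test. The deadline still matters, because it rules out testing after a V0 signature.
3. **The tests may be routine care.** The sites are general practices, and candidates must have been symptomatic for at least two seasons. Section 1.3 says the study requires no invasive procedure, which is consistent with the authors regarding the tests as outside the study. This stands as a real uncertainty. The protocol does not separate routine tests from tests done to establish eligibility, although the flow-chart row in which they appear concerns selection and criteria verification.
4. **The consent form itself cannot be seen.** It may mention screening tests. That would not alter the timing of its signature.

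What remains of the objection is that the number affected is unknown and could be zero, and that the protocol does not expressly direct testing without consent. The point is therefore conditional: such a test could precede consent.

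**Conclusion.** The concern holds. For a candidate who needs a new allergy test, following the synopsis, 4.2 and 6.2 as written puts the test before the signature, by a nominal one month, and section 9.4 does not remedy this.

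The conclusion rests on two conditions: that some candidates arrive without a qualifying result, which the flow chart itself provides for, and that at least some of their tests are done for the trial and not as routine care, which the protocol leaves open. Confidence is medium for that reason. The correction should be made because it is cheap and concerns consent. It alters no statistical figure: sample size and the primary analysis are unaffected.

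**What to change.** - **Section 6.2:** state that the consent form is signed before any allergy test performed for the study, after information and time for reflection. Allow signature at Screening or at any point before V0, and mark the flow chart accordingly.
- **Existing results:** continue to accept results already obtained in routine care, with no earlier signature needed. Keep the eligibility check at V0.
- **Synopsis, 4.2 and 6.1:** use one common test deadline that fits this order, so that a candidate who signs between Screening and V0 can still be tested before the V0 eligibility check.
- **Section 1.3 (minor):** mention the possible skin or blood test.

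The cost is a flow-chart and wording amendment. Nothing changes for candidates with a qualifying result. Those who need a new test have either less time to reflect, if they sign at Screening, or one extra contact before V0.
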